Trial Title: Screening with Tampons: Evaluating Diagnostic Accuracy for STIs, BV and HPV and Assessing Participant Views

Short title: STAMP

Ethics Ref: 23/LO/0882

IRAS Project ID: 334064

Protocol Number: LH-DA-01

Date and Version No: v3.0 29 Nov 2023

Chief Investigator: [name] [name], Lindus Health, [name]
[name],
[name]

Investigators: [name], Careggi University
Hospital in Florence

Sponsor: Tampon Innovations LTD, [name],
Bulgaria

Funder: Tampon Innovations LTD, [name],
Bulgaria

**Chief Investigator
Signature:**

Confidentiality Statement

This document contains confidential information that must not be disclosed to anyone other than the Sponsor, the Investigator Team, HRA, host organisation, and members of the Research Ethics Committee and Regulatory Authorities unless authorised to do so.

Protocol signatures

Protocol Title: STAMP: Screening with Tampons: Evaluating Diagnostic Accuracy for STIs, BV and HPV and Assessing Participant Views

Protocol Date and Version No: V3.0 29 Nov 2023

Protocol signature page

The undersigned has read and understood the trial protocol detailed above and agrees to conduct the trial in compliance with the protocol.

Principal Investigator (Please print name)	Signature	Site name or ID number	Date
---	-----------	---------------------------	------

Following any amendments to the protocol, this page must be updated with the new protocol version number and date and re-signed by the site PI.

Protocol Synopsis

Protocol Title	STAMP: Screening with Tampons: Evaluating Diagnostic Accuracy for STIs, BV and HPV and Assessing Participant Views
Protocol Version and Date	V3.0 29 Nov 2023
Protocol Number	LH-DA-01
Sponsor	Tampon Innovations LTD, which is a subsidiary of DAYE
CRO	Lindus Health
Trial Design	Diagnostic trial comparing the diagnostic accuracy of the DAYE Diagnostic Tampon (DDT) with a vaginal swab (self-collected and clinician taken).
Location	UK and Italy
Recruitment Strategy	Participants will be recruited centrally or via site visits. Participants will be identified via primary care, advertising on social media and to patient communities, or via clinic lists and clinic visits at a trial site.
Trial Aims	
 ● To measure the diagnostic accuracy of the diagnostic tampon in a diverse population of people assigned female at birth. ● To compare the performance of the diagnostic tampon with traditional diagnostic methods to identify potential advantages and challenges. ● To assess the acceptability and usability of the diagnostic tampon among the target population and explore feasibility and clinician acceptability of the diagnostic tampon in clinical practice among key stakeholders. ● To provide evidence-based recommendations for the integration and sustainability of the diagnostic tampon into current health practices.
Trial Objectives	
Primary Objective:
 
 ● Evaluate the diagnostic accuracy of the Daye

	
diagnostic tampon for detecting Chlamydia, Gonorrhoea, BV and HPV, specifically demonstrating a sensitivity of more than 70% for DDT.
 
Secondary objectives:
 
 ● Assess the usability of the DDT (via ASQ). ● Explore participants' views of the usability and acceptability of the DDT. ● Assess whether the DDT is a preferred sampling method for participants. ● Assess if the order of sample collection (self-swab vs DDT) impacts diagnostic accuracy. ● Understand the health economic consequences of using the DDT for STI, BV and HPV testing. ● Explore stakeholder attitudes to tampons as a means of sample collection for microbial testing. ● Assess the occurrence of AEs/SAEs as a result of tampon sampling. 
Exploratory objective:
 
 ● Explore the relationship between duration of wear and diagnostic accuracy.
Sample Size	
350 participants
 
Group 1: 50 participants with a recent confirmed HPV+ diagnosis (UK and Italy)
 
Group 2: 300 participants from the general population (UK only)

Procedures	
All participants will have 3 samples taken: the DAYE Diagnostic Tampon (DDT), a vaginal self-swab and a clinician taken vaginal swab that is validated for use for the downstream microbial test.

Randomisation	
All participants will be randomised using block randomisation according to sample order for the DDT and self-swab:
 
 ● Group A: Approximately half the participants will perform the self-swab followed by the DDT. ● Group B: Approximately half the participants will perform the DDT followed by the self-swab
Daye Diagnostic	
The DAYE Diagnostic Tampon is a class A in vitro diagnostic

Tampon	device. It has CE certification (self-certified via a declaration of conformity, following the IVDR (EU) 2017/746).
Eligibility	
Inclusion Criteria
 
 1. Individuals aged 25–65 years. 2. People assigned female at birth (AFAB). 3. Sexually active individuals. 4. Group 1 only: Confirmed HPV+ diagnosis within the past 4 weeks. 
 a. UK only: Ability to upload evidence of this diagnosis to the trial ePRO system (e.g. via a screenshot of the NHS app, or similar to be reviewed by the trial team). 5. Willingness to give informed consent and adhere to trial procedures. 
Exclusion Criteria
 
 1. Previous hysterectomy or total hysterectomy with removal of cervix 2. Known allergy or sensitivity to tampons 3. History of TSS (both tampon-associated and non-tampon associated) 4. Individuals who are pregnant or breastfeeding. 5. Participation in another interventional clinical trial or use of investigational drugs in the last 30 days. 6. Any other significant disease or disorder which, in the opinion of the Investigator, may either put the participants at risk because of participation in the trial, or may influence the result of the trial, or the participant’s ability to participate in the trial.

To enquire about the trial, contact the STAMP Trial Team:

STAMP Trial

Lindus Health

Email Address: [contact]

TABLE OF CONTENTS

[consent](#)

[1. BACKGROUND AND RATIONALE](#)

[1.1 Background](#)

[1.2 Rationale](#)

[1.3 Clinical Studies](#)

[2. OBJECTIVES AND OUTCOME MEASURES](#)

[3. TRIAL DESIGN](#)

[3.1. Participant Flowchart](#)

[3.1.1 Central Recruitment](#)

[3.1.2 Site Recruitment](#)

[4. PARTICIPANT IDENTIFICATION](#)

[4.1. Trial Participants](#)

[4.2. Inclusion Criteria](#)

[4.3. Exclusion Criteria](#)

[5. TRIAL PROCEDURES](#)

[5.1. Schedule of Assessments](#)

[5.1.1 Schedule of Assessments – Central recruitment or site recruitment from clinic lists](#)

[5.1.2 Schedule of Assessments – Clinic recruitment \(via in person clinic visits\) – Italy Only](#)

[5.2. Recruitment](#)

[5.2.1 Recruitment at sites](#)

[5.2.2 Central recruitment](#)

[5.2.2 Participant Payments](#)

[5.3. Pre-screening](#)

[5.4. Informed Consent](#)

[5.5. Screening and Eligibility Assessment](#)

[5.5.1. Screening and Eligibility Completed Centrally](#)

1. BACKGROUND AND RATIONALE

1.1 Background

Medical innovations routinely misunderstand and under-serve women's bodies and minds. This is unsurprising, as guidelines (EU/UK) and regulation (US) on inclusion of women as participants in modern medical research were only brought in during the 1990s. There is therefore a large gap in medical research available for a range of gynaecological conditions.¹

Sexually Transmitted Infections (STIs), Human Papillomavirus (HPV) and vaginal infections are a serious threat to gynaecological health, with pelvic inflammatory disease, Cervical Cancer (CC), and infertility among the risk factors.^{2,3} However 70% of gynaecological infections are asymptomatic and may remain undiagnosed.⁴ Early detection of HPV, CC and STIs often leads to successful management and full recovery. Healthcare systems are struggling to increase testing uptake for HPV. Even before COVID disrupted screening programmes uptake was as low as 25% in many EU countries.⁵ Clinician-taken swabs lead to higher healthcare costs and have a historically low uptake, limiting early STI and HPV detection. Challenges include emotional barriers and practical impediments such as embarrassment, discomfort, time constraints, and a labour-intensive collection process.⁶

Currently the process of screening and treatment of STIs, Bacterial Vaginosis (BV) and HPV through public healthcare services is very disjointed. While menstrual tampons are a novel method for sample collection, they are already widely used on a monthly basis by 85–90% of pre-menopausal women in western Europe, the UK, and the US.⁷ They offer high absorbency and familiarity, making them a promising tool for sample collection.^{8,9} Their utilisation could enhance screening accessibility, especially for women facing barriers such as cost, stigma, or inconvenience.

Developing a sensitive and user-friendly diagnostic tool using menstrual tampons could significantly improve women's health outcomes, reducing the incidence of HPV and STI-related cancers. Leveraging the convenience and familiarity of tampons may increase screening uptake and enhance early detection and treatment of STIs.

The Daye Diagnostic Tampon (DDT) is an at-home-based gynaecological test kit, using a menstrual tampon for sample collection. The DDT can be sent in a screening kit to the participants home and needs to be worn for a minimum of 20 minutes to collect a potent sample.

This trial aims to assess the feasibility and accuracy of using menstrual tampons as a specimen collection device for HPV, BV and STI testing, comparing it to self-collected and clinician-collected swabs. This method of testing offers an alternative to traditional methods like urine or blood samples that may not be accessible or convenient for everyone. By increasing testing rates and improving early detection, the use of menstrual tampons has the potential to enhance healthcare outcomes.

1.2 Rationale

Vaginal health screening often has very low uptake, meaning that most women are unaware of their HPV, BV and STI status. Knowledge of HPV status could encourage uptake of preventative treatments (such as HPV vaccine) and uptake of screening for cervical cancer. Cervical cancer is one of the most preventable and curable forms of cancer as long as it is detected early and managed effectively.¹⁰ The Daye Diagnostic Tampon offers a preferred sampling method for screening which will help improve uptake of testing and enable timely diagnosis and treatment.

1.3 Clinical Studies

Preliminary research conducted by Daye has shown that self-collected tampons exhibit diagnostic accuracy on par with clinician-collected swabs for detecting HPV, BV and STIs. In this pilot work, Hologic Aptima swabs were the sample collection device selected as they are designed to optimise efficiency and accuracy of the PCR assays developed by Hologic.

Encouragingly, participants express a preference for tampon self-collection (90%) over clinician-collected swabs. However, future research involving larger and diverse participant groups is required to validate these outcomes and guide the implementation of tampon-based self-collection programs for cervical cancer screening and STI testing.

Daye's Pilot HPV Study (currently pending publication)

Daye conducted a comparative analysis of the DDT and traditional Health Care Worker (HCW)-collected cervical swabs. In a cohort of 60 participants, the study utilised real-time PCR technology to assess the detection efficiency for HPV and STIs.

Participants provided informed consent and underwent both clinician-collected and self-collected sample collection using the Daye Diagnostic Tampon. Acceptability was

assessed through a questionnaire with Likert-scale responses.

Study Design and Methods:

In the clinical stage, two arms were employed to compare different specimen collection methods. In the Reporting Arm, healthcare workers collected cervical and low vaginal specimens from the participants. In the Experimental Arm, participants used self-collected tampons to obtain their samples. These samples were then divided into two types of collection containers: the ThinPrep Vial (TP Vial) or the Aptima Multitest Swab Collection Kit (APTIMA). After collection, the samples were stored at room temperature for 4–6 weeks before RNA isolation. Each arm collected a total of 120 samples.

Results:

Among the 60 participants who completed the study, the self-collected tampons demonstrated sensitivity and specificity of 66.67% (95% CI: 22.3%–95.7%) and 90.74% (95% CI: 79.7%–96.9%) when using TP Vial and 83.33% (95% CI: 51.6%–97.9%) and 85.42% (95% CI: 72.2%–93.9%) when using APTIMA for HPV detection, respectively. For BV detection, the tampons exhibited sensitivity and specificity of 100.0% (95% CI: 51.8%–99.7%) and 96.43% (95% CI: 87.7%–99.6%) (TP Vial) and 88.89% (95% CI: 22.3%–95.7%) and 98.04% (95% CI: 89.06%–100.0%) (APTIMA), respectively. For APTIMA Combo 2 (AC2) detection (for chlamydia and gonorrhoea), sensitivity and specificity were 100.00% (95% CI: 2.5%–100.0%) and 100.0% (95% CI: 93.9%–100.0%) (TP Vial) and 100.00% (95% CI: 2.5%–100.0%) and 98.31% (95% CI: 90.9%–100.0%) (APTIMA), respectively. Notably, 90% of participants expressed a preference for tampon self-collection over clinician-collected swabs.

Conclusion:

Self-collected tampons demonstrated comparable diagnostic accuracy to clinician-collected swabs for HPV and STI detection. The tampon self-collection method was well-accepted and preferred by participants, suggesting its potential as an alternative screening tool, particularly in low-resource settings. Further research with larger and more diverse populations is recommended to validate these findings and inform tampon-based self-collection programs for cervical cancer screening.

2. OBJECTIVES AND OUTCOME MEASURES

Primary Objective

Objective	Outcome Measure	Timepoint(s) of evaluation
Evaluate the diagnostic accuracy of the Daye Diagnostic Tampon for detecting Chlamydia, Gonorrhoea, BV and HPV, specifically demonstrating a sensitivity of more than 70% for DDT.	Accuracy of the STI, BV and HPV testing using menstrual tampons compared to other specimen collection methods (clinician taken and self-swab) using the following assays: 
 - Hologic's APTIMA HPV (for HPV) - Hologic's APTIMA AC (for chlamydia and gonorrhoea) - Cepheid MPV assay (for BV) 	Within 4 weeks of the samples being received at the lab.

Secondary Objectives

Objective	Outcome Measure	Timepoint(s) of evaluation
Assess the usability of the DDT (via ASQ)	After scenario questionnaire scores	Post-sampling (once all samples are collected)
Explore participants views of the usability and acceptability of the DDT	Quantitative and qualitative feedback from pre- and post-sampling questionnaires and focus groups	Pre-sampling (baseline) and Post-sampling (once all samples are collected)
Assess whether the DDT is a preferred sampling	User preferences (self-report)	Pre-sampling (baseline) and Post-sampling (once

method for participants		all samples are collected)
Assess if the order of sample collection (self-swab vs DDT) impacts diagnostic accuracy	Diagnostic accuracy	Post sample analysis
Understand the health economic consequences of using the DDT for STI, BV and HPV testing	Willingness to pay for the DDT, comparison of time taken for DDT vs clinician swab	Post-sampling (once all samples are collected)
Explore stakeholder attitudes to tampons as a means of sample collection for microbial testing.	Qualitative feedback from stakeholder questionnaires	Ongoing throughout the trial once stakeholders have engaged with the tampon
Assess the occurrence of AEs/SAEs as a result of tampon sampling.	AE/SAE occurrence.	None expected, but any events will be collected and recorded on an ongoing basis as outlined in section 7.

Exploratory Objective

Objective	Outcome Measure	Timepoint(s) of evaluation
Explore the relationship between duration of wear and diagnostic accuracy.	Duration of DDT wear and diagnostic accuracy	Post sample analysis

3. TRIAL DESIGN

A diagnostic trial comparing the diagnostic accuracy, usability and acceptability of the DAYE Diagnostic Tampon (DDT) compared to standard vaginal self-swabs and clinician administration of a vaginal swabs. Diagnostic accuracy will be compared for detection of Chlamydia, Gonorrhoea, BV & HPV.

A total of 350 eligible participants will be enrolled into the trial in the UK and Italy. To adequately assess DDT performance on specificity and sensitivity, participants will be recruited from one of two groups:

- Group 1: 50 participants with a recent confirmed HPV diagnosis (UK and Italy)
- Group 2: 300 participants from the general population (UK only)

All participants will be randomised according to sample order for the DDT and self-swab using block randomisation:

[figure not shown]
- Group A: Approximately half the participants will perform the self-swab followed by the DDT.
- Group B: Approximately half the participants will perform the DDT followed by the self-swab

Pre-screening, informed consent, screening and eligibility assessments may occur online or in person. Randomisation will be performed at the point of enrolment by a member of the trial team using a pre-generated list of treatment allocation blocks. Some demographic information and medical history will be collected at baseline. All eligible participants will be provided with a trial kit containing the DDT and self-swab and attend at least 1 clinic visit where they will have a clinician taken vaginal swab as part of their participation in the trial. Participants will also provide answers to questionnaires at baseline and after all sampling is complete. Participants will enter data directly into the EDC platform or via paper questionnaires completed in-person at the clinic visit and entered into the EDC platform by trained staff. Participation in the trial is expected to last approximately 2-4 weeks (dependent on timing of clinic appointment(s)). All samples collected during the trial will be sent to a central accredited laboratory for analysis, either in the UK or Italy i.e., samples will be analysed in the country they were collected.

[figure not shown]
3.1. Participant Flowchart

Two participant flows are presented below. The central recruitment flow shows the participant flow from recruitment from patient outreach (e.g. social media, advertising to patient networks, clinic outreach to patient lists). The site recruitment flow shows the options for participant flow when participants are recruited in person via a site.

3.1.1 Central Recruitment

3.1.2 Site Recruitment

4. PARTICIPANT IDENTIFICATION

4.1. Trial Participants

Participants will be sexually active individuals assigned female at birth (AFAB) aged 25–65. A subset of participants (Group 1) will have had a recent HPV diagnosis. All inclusion and exclusion criteria refer to both Group 1 and Group 2 unless specifically stated.

4.2. Inclusion Criteria

Participants must meet all the following criteria:

1. Individuals aged 25–65 years.
2. People assigned female at birth (AFAB).
3. Sexually active individuals. In this case, “sexually active” is defined as having penetrative vaginal sex.
4. **Group 1 only:** Confirmed HPV+ diagnosis within the past 4 weeks.
 - a. *UK only:* Ability to upload evidence of this diagnosis to the trial ePRO system (e.g. via a screenshot of the NHS app, or similar to be reviewed by the trial team).
5. Willingness to give informed consent and adhere to trial procedures.

4.3. Exclusion Criteria

The participant may not enter the trial if ANY of the following apply:

1. Previous hysterectomy or total hysterectomy with removal of cervix
2. Known allergy or sensitivity to tampons
3. History of TSS (both tampon-associated and non-tampon associated)
4. Individuals who are pregnant or breastfeeding.
5. Participation in another interventional clinical trial or use of investigational drugs in the last 30 days.
6. Any other significant disease or disorder which, in the opinion of the Investigator, may either put the participants at risk because of participation in the trial, or may influence the result of the trial, or the participant’s ability to participate in the trial.

5. TRIAL PROCEDURES

5.1. Schedule of Assessments

5.1.1 Schedule of Assessments – Central recruitment or site recruitment from clinic lists^a

Contact Type	Pre-screening	Screening	Screening +1	Baseline	Pre Trial Visit	Trial Visit	Post Trial Visit
Contact time	Pre-screener accessed via participant outreach	Immediately following successful pre-screening	Normally within 1 working day of screening	Provided once enrolment confirmed	Approximately 24 hours before clinic visit		Immediately following trial visit once all sampling is complete
Assessments							
Pre-screen via trial website	✓						
Written informed consent	✓						
Eligibility assessment ^b		✓					
Eligibility review, trial "greenlight" & enrolment ^c			✓				
Randomisation			✓				
Medical history ^b				✓			
Demographics ^b				✓			
Sampling							
DDT					✓		
Self-swab					✓		

Contact Type	Pre-screening	Screening	Screening +1	Baseline	Pre Trial Visit	Trial Visit	Post Trial Visit
Contact time	Pre-screener accessed via participant outreach	Immediately following successful pre-screening	Normally within 1 working day of screening	Provided once enrolment confirmed	Approximately 24 hours before clinic visit		Immediately following trial visit once all sampling is complete
Assessments							
Clinician swab						✓	
Return of completed DDT/Self-Swab						✓	
Questionnaires^d							
Pre-sampling questionnaire				✓			
Post-sampling questionnaire							✓
Safety							
AEs and SAEs ^e					✓	✓	✓

^a This schedule also applies where a site has contacted participants from clinic lists in advance of visits and provided them with the pre-screening link.

^b Key demographic and medical history data will be verified during the eligibility assessment to ensure suitability for inclusion. Detailed demographic and medical history data is collected following enrollment.

^c Greenlight will be given once the trial team has reviewed eICF and participant reported eligibility.

^d Questionnaires will be emailed directly to participants and completed via Citrus ePRO.

^e Self-reported by participant as required.

5.1.2 Schedule of Assessments – Clinic recruitment (via in person clinic visits) – Italy Only

Contact Type	Screening	Baseline	Trial Visit 1	Pre Trial visit 2	Trial visit 2	Post Trial Visits
Contact time	At clinic visit	Provided once enrolment is confirmed	Continuation of screening visit	Approximately 24 hours before clinic visit		Immediately following trial visit once all sampling is complete
Assessments						
Written informed consent	✓					
Eligibility assessment ^a	✓					
Trial “greenlight” & enrolment ^b	✓					
Randomisation	✓					
Medical history ^a		✓				
Demographics ^a		✓				
Sampling						
DDT				✓		
Self-swab				✓		
Clinician swab			✓			
Return of completed DDT/Self-Swab					✓	
Questionnaires^c						
Pre-sampling questionnaire		✓				
Post-sampling questionnaire						✓
Safety						
AEs and SAEs ^c			✓	✓	✓	✓

^a Key demographic and medical history data will be verified during the eligibility assessment to ensure suitability for inclusion. Detailed demographic and medical history data is collected following enrollment

^b Greenlight will be given once screening is completed during the clinic visit.

^c Questionnaires will be completed on paper and entered into the trial database by suitably qualified members of the trial team..

^d Self-reported by participant as required.

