5.11. Questionnaires

A pre-sampling questionnaire will be sent to the participant upon enrolment before any samples have been taken. This questionnaire will assess the participants initial views on the DDT in advance of sampling. This questionnaire must be completed prior to the participant having any samples taken.

A second questionnaire (post-sampling questionnaire) will be sent to the participant following their clinic appointment(s) once all samples have been taken. This

questionnaire should only be completed once all other trial procedures have been performed. This questionnaire will compare the participants' experiences with the DDT versus the standard self-swab and clinician swab methods.

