7.3. Procedures for Reporting Adverse Events

We do not anticipate that the trial procedures (DDT or swabs) should result in any adverse events (AEs) but include this section in case such events are reported so that they can be considered for causal links to the trial procedures. Only AEs that are clinically judged by the research site PI as being caused by the trial procedures (related and unexpected) will be reported to the REC that gave favourable opinion.

Participants will be provided with contact information for the trial team and the clinic nurse in the event that they need to report a side effect or medical event from the DDT, self-swab or clinician swab.

Events related to the trial procedures will be collected from the collection of the first trial sample until the final questionnaire is submitted.

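### Adverse event frequency is a secondary endpoint, but the only capture route the protocol describes is participant-initiated self-report, so a low or zero count could not be read as absence of events

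*Protocol*

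**What the plan says.** Section 2 lists as a secondary objective: "Assess the occurrence of AEs/SAEs as a result of tampon sampling". The time point entry reads: "None expected, but any events will be collected and recorded on an ongoing basis as outlined in section 7". Section 8.2.2 then plans a descriptive analysis giving the number and percentage for each event.

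On how events are obtained:

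- **Schedule 5.1.1** (central recruitment, or recruitment from clinic lists): the AE/SAE row is ticked before, at and after the trial visit. Its footnote e reads "Self-reported by participant as required".
- **Schedule 5.1.2** (in-person clinic recruitment, Italy): the row is ticked at Trial Visit 1, before and at Trial Visit 2, and after the visits. The same wording appears as footnote d, but the row carries marker c, which is the footnote on paper questionnaires. Footnote d has no marker in the table.
- **Section 7.3**: participants are given a way to get in touch with the study staff should they have a problem to raise after any of the three sampling methods. It also sets the window: "Events related to the trial procedures will be collected from the collection of the first trial sample until the final questionnaire is submitted".
- **Section 5.10**: the only assessment listed for the clinic visit is the clinician swab.
- **Section 5.11**, on the post-sampling questionnaire: "This questionnaire will compare the participants' experiences with the DDT versus the standard self-swab and clinician swab methods". No adverse event item is mentioned.

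**The concern.** A frequency needs a numerator obtained in the same way from everyone in the denominator. Here the denominator would be all participants, while the numerator as described contains only those who chose to come forward. Participants who had no event and participants who had one and did not mention it look identical in the data.

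The loss would probably be selective. Troublesome events tend to be volunteered, while mild ones such as discomfort on removal or transient irritation tend not to be. The tampon is used at home, so staff do not observe its use.

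Section 7.3 also limits collection to events related to the procedures, whereas section 7.2 gives the judgement of relatedness to a medically qualified person. Under self-report, the participant makes the first cut.

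The protocol expects no events. That expectation is what the objective should be able to test, and passive capture tests it poorly. What is at stake is the interpretation of this secondary endpoint. The primary accuracy analyses are not affected.

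**Working it through.** The protocol states no expected adverse event rate and no reporting rate, so there is no planned figure to reproduce. The main check is textual, and the arithmetic is only illustrative.

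**Step 1: is anyone described as asking?**

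| Contact | What the protocol describes | AE question described? |
|---|---|---|
| Home sampling | Tampon and self-swab, unsupervised (5.9, 6.1, 6.2) | No |
| Clinic visit | Clinician swab; return of home samples (5.1.1, 5.10) | No; row ticked, footnote says self-report |
| Post-sampling questionnaire | Comparison of experiences across methods (5.11) | No |
| Any time in the window | Contact details supplied (7.3) | No; participant-initiated |

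**Step 2: which visits can yield tampon events?** In 5.1.1 the Trial Visit comes about a day after home sampling, so it can. In 5.1.2 the clinician swab is taken at Trial Visit 1, before the tampon is used. That visit can cover only the swab, and tampon events can first be asked about at Trial Visit 2.

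**Step 3: what a zero count would exclude.** Inputs: n = 350 (section 8.3) and f, the share of events that are reported (assumed; not in the protocol).

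- Upper one-sided 95% limit on the recorded risk with zero events: 1 − 0.05^(1/350) = 0.00852, or 0.85%.
- If only a share f is reported, the recorded risk is p × f, so the limit on the true risk p is 0.00852 / f.
 - f = 1: 0.85%
 - f = 0.5: 0.00852 / 0.5 = 1.7%
 - f = 0.25: 0.00852 / 0.25 = 3.4%

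**Step 4: chance of recording no event at all.** P(zero) = (1 − p × f)^350, with both p and f assumed.

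| True risk p | f = 1 | f = 0.5 | f = 0.25 | f = 0.1 |
|---|---|---|---|---|
| 1% | 3% | 17% | 42% | 70% |
| 5% | about 0% | about 0% | 1.2% | 17% |

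At p = 5% and f = 0.25, the expected number recorded is 350 × 0.05 × 0.25 = 4.4. Incomplete reporting weakens what a low count can exclude, but it does not make a zero count certain.

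**The case against.** The strongest reply is that the text does not rule out solicitation. The protocol uses self-report elsewhere for answers that are asked for (eligibility in 5.5.1, preferences in section 2). The AE row is ticked at scheduled contacts, and 7.3 says that related events will be collected up to the final questionnaire. In 5.1.2 the row's marker, read literally, points to the questionnaires. The questionnaire and case report form are not shown. This stands to the extent that the claim must be that the protocol *describes* no solicited question, not that none exists. It does not remove the point: the footnote qualifies self-report with as required, and 7.3 describes a route that the participant has to start.

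A reader might infer that staff see nothing unless they ask. The documents do not support that. Staff receive the used tampon, and in 5.1.1 a clinician takes a high vaginal swab the day after home sampling, so a tampon not returned or a visible problem could be noticed. That is incidental observation, though, and it does not reach symptoms that have resolved or are not visible.

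A reader might also infer that early detection of Toxic Shock Syndrome (7.6) is weakened. That is not shown. The contact route in 7.3 is open throughout the window, and one question about a day later would add little to it.

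Finally, the analysis is descriptive, with no threshold or safety claim attached, and the device is a class A in vitro diagnostic. That limits the consequences. It does not make an uninterpretable frequency useful.

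**Conclusion.** The point holds in this form: AE/SAE occurrence is a secondary endpoint reported as frequencies, the only collection method described is participant-initiated, and a low or zero count obtained that way could not be read as absence of events. It is worth changing because the remedy uses contacts that already exist.

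The size is illustrative only. With zero events in 350, the excluded true risk moves from 0.85% to about 1.7% or 3.4% if half or a quarter of events are volunteered. Those shares are assumptions. The calculation also takes all 350 participants as providing data and one reporting probability for every event.

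The stronger reading, that events will be under-ascertained and the endpoint will come out as none, is a prediction the documents cannot carry. They give neither an event rate nor a reporting rate, and with a 5% risk and 25% reporting a zero count would be unlikely (1.2%). Nor can it be said that every participant completes the post-sampling questionnaire, since section 8.8 foresees missing ones. That is a reason to ask at the visit as well.

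**What to change.** - **Both schedules and 7.3:** replace the passive footnote with a standard adverse event question put to every participant at the first existing visit after home sampling. This is the Trial Visit in 5.1.1 and Trial Visit 2 in 5.1.2; Trial Visit 1 in 5.1.2 can cover only the clinician swab. Put the same question in the post-sampling questionnaire, which also covers site-recruited participants for whom a second visit is not held (5.10 makes it optional). Keep spontaneous reporting.
- **5.10 and 5.11:** name the question among the visit assessments and the questionnaire content. If the forms already contain one, say so.
- **8.2.2:** give the number of participants asked as the denominator.
- **5.1.2:** correct the AE row, which carries marker c, and attach footnote d or its replacement.

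The cost is a few questionnaire items and a short question at an existing visit, with no new visit. The downside is that more minor events will be recorded, so the frequency will look less favourable.

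If solicitation is not adopted, label the frequencies in 8.2.2 as spontaneously reported events and state that a zero count is not evidence of absence.
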